Botulinum neurotoxin A is one of the seven neurotoxins produced by *Clostridium botulinum*.¹⁹⁻²⁰ When injected into the muscle, it binds very specifically to the presynaptic membrane of motoneuron nerve endings and produces chemodenervation that can last for 14 to 16 weeks²¹⁻²². This long-lasting neuromuscular blockade is achieved through the cleavage of nine amino-acid residues from the carboxyl terminus of synaptosome-associated protein with relative molecular mass 25K (SNAP-25)²⁴⁻²⁵. As a consequence, acetylcholine-containing synaptic vesicles can no longer fuse with the plasma membrane, resulting in the blockade of neurotransmission. The injected muscles become weak over 2-20 days and may recover over 2-4 months as new terminal axons sprout and restore neurotransmission.²³

Botox was first documented for use in the treatment of anismus in 1988, with a symptomatic improvement in 4 of 7 patients (57%) at 4 weeks after the injection²⁸. This was a pilot study and different doses of Botox were used. Two patients developed fecal incontinence that disappeared once the effect of Botox started to fade.

Several phase I and II trials since then demonstrated that Botox is a safe and effective therapeutic approach for ODS²⁸⁻³⁵. There were no severe adverse effects and the overall mortality rate was 0% in all of these studies. Subject to the caveats that the majority of these studies were uncontrolled, with small sample sizes, variable doses, primary outcomes and administration modalities of Botox, their encouraging results led to Botox being increasingly used off-label for patients with pelvic floor disorders who failed medical management and biofeedback therapy. It offers significant advantage in the fact that it can be administered in one session in the office.

Joo et al. ³¹ injected a dose of Botox contingent with body mass (a total of 12-30 units) in 4 patients with anismus who had failed biofeedback therapy. Symptomatic improvement was noted in all subjects (100%) at 1 and 3 months after the injection. The effect was maintained at one year in 50% of their patients. Shafik and El-Sibai³⁵ injected 25 IU of Botox in the external anal sphincter of 15 patients with nonrelaxing puborectalis muscle syndrome. Straining at defecation disappeared and stool frequency normalized in 13 of 15 patients (87%) with a mean duration of effect of 4.8 +/- 1.4 SD months. None of the patients treated with Botox reported any adverse effects after the injection.

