In 2006, Maria et al. ³⁰ injected 60 IU of Botox in the nonrelaxing puborectalis muscle of 24 patients with chronic outlet obstruction constipation. At 2 months, 19 of 24 patients (79%) had symptomatic improvement. The other five patients who did not respond to the first dose were offered a rescue treatment with 100 IU of Botox. All of them had symptomatic improvement after two months and this improvement persisted to the end of follow-up. At 4 months, 4 of the 19 patients (21%) who initially improved suffered symptomatic recurrence and were successfully retreated with 100 IU of Botox. At an average follow-up of 39+/-17 months, there was no symptomatic recurrence in any of the 24 patients. Two patients (8%) had mild flatus incontinence after the first injection, but there were no other short- or long-term complications or side effects.

Ron et al³² randomized 25 patients with anismus to receive 20 IU of Botox with two different methods of administration (local injection of Botox-10 units to each side of the puborectalis or 20 units to the posterior aspect of this muscle). Only 29% had a symptomatic improvement in straining index after this dose and the overall satisfaction rate with the treatment was 58%. The reported adverse effects were: 0% incontinence, local infection or bleeding (these remained the same during follow-up after the 1st and 2nd injection). 12.5% of all patients developed mild pain after injection that increased at follow-up.

Faried et al. ²⁹ randomized sixty patients with anismus to receive biofeedback therapy, 100 IU of Botox or posterior division of the puborectalis muscle in. The groups differed significantly in terms of clinical improvement at 1 month (50% for biofeedback, 75% Botox injection, 95% posterior division of the puborectalis muscle, p=0.006). The symptomatic improvement persisted at 1 year in 30% of patients in the biofeedback group, 35% in the Botox group and 70% in the surgery group (p=0.02). No adverse effects were reported for the Botox arm. Two patients in the surgery arm developed incontinence, compared to 0 patients in the Botox and biofeedback arms.

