For both groups, the interventions will be administered in the office under local anesthesia with 0.25% Marcaine stored in the clinic at 20° to 25°C. We plan to use a 10 mL single dose vial of Marcaine (Bupivacaine Hydrochloride Injection, USP 0.25% (2.5 mg/mL)) administered as local infiltration. More or less drug may be used depending on each individual case. The MGH **Research** Pharmacy will perform the computerized randomization and send up medication or saline in paper bag based on randomization of the subject. Both saline and Botox will be brought from research pharmacy on the day of the procedure in a brown paper bag.

The PI will use transanal ultrasound to clearly identify the puborectalis muscle. Once the muscle is identified, a 23-G needle will be used to inject the agent transanally into the puborectalis and external anal sphincter in three separate locations.

c. Data to be collected

All data are collected prospectively, at the pre-specified time points according to the protocol. All data will be collected in questionnaires attached (see above for specific description). Data from baseline manometry will be taken from patient chart and recorded into REDCap database where data will be stored. Anorectal manometry from 1-month follow-up will also be stored in REDCap database.

VI. BIOSTATISTICAL ANALYSIS

a. Specific data variables being collected for the study

Data collection sheets are attached to this submission. They include the MRN to facilitate data extraction, demographic information (age, sex, race), diagnostic tests at baseline and the study endpoints collected at pre-specified times.

b. Study Endpoints

a) Primary endpoint:

Baseline to 1 month after treatment changes in the sum of Altomare ODS score (ODS-S) and Patient Assessment of Constipation- Quality of Life score (PAC-QoL)

b) Secondary endpoints:

- Baseline to 1, 3, 6 and 12 months after treatment changes in Altomare ODS score (ODS-S) and Patient Assessment of Constipation- Quality of Life score (PAC-QoL)
- Changes in the generic SF-36 version 1, Cleveland Clinic Fecal Incontinence Score (CCFI) and Fecal Incontinence Quality of Life Scale (FIQoL) at 1, 3, 6 and 12 months from baseline
- Relaxation of puborectalis with push measured by EMG at 1 month
- Balloon expulsion test at 1 month
- Manometric changes at 1 month- changes in anal sphincter function (resting sphincter pressure, maximal resting anal pressure, maximum squeeze pressure).

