- Change in defecation index [Time Frame: Baseline, 1 month follow-up visit]. The defecation index=maximum rectal pressure during attempted defecation/minimum anal residual pressure during attempted defecation. This is calculated based on measurements obtained from anorectal manometry and is a measure of treatment efficacy.

c. Statistical methods

All analysis will be based on intention-to-treat population in that all randomized subjects will be included in the analysis.

Data will be expressed as mean+/- standard deviation (SD) for all continuous outcomes, and as counts and proportions for all categorical outcomes. The primary analysis (i.e., the comparison of 1-month change in mean ODS-S and PAC-QoL between the 2 treatment arms) will be made by independent samples t-test. Comparison of treatment effect over time (i.e., 1- and 3-, 6- and 12 months) on all scale scores will be performed by using longitudinal linear mixed effects model, which allows to specify the subject specific baseline levels and the time dependent response trajectories (i.e., slopes) random (SAS proc mixed). All p-values are two-tailed and considered significant if p<0.05.

d. Power analysis

The proposed sample size is 46 (i.e., 23 in each treatment arm). With an assumption of an attrition rate of up to 15%, we anticipate to attain 40 study completers. The study is designed to detect at

least 25% decrease in mean ODS-S and PAC-QoL at 1 month after treatment with Botox with 80% power at a 5% significance level. This effect size of \geq 25% is equivalent to a decrease in mean ODS-S decrease from 15 points at baseline to \leq 11.4 points at 1 month³⁷⁻³⁸. **VII. RISKS AND DISCOMFORTS**

a. Complications of surgical and non-surgical procedures

We do not expect any unusual safety concerns in this study. The small foreseeable discomforts and complications will be treated as per standard of care.

b. Drug side effects and toxicities

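### The 3-, 6- and 12-month score comparisons rest on a random-slope model with no stated visit terms; fitted as a straight line from baseline, it would misestimate an early-onset effect

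*Combined protocol and SAP*

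**What the plan says.** Section VI.b defines the secondary score endpoints by visit: "Baseline to 1, 3, 6 and 12 months after treatment changes in Altomare ODS score (ODS-S") with PAC-QoL, and likewise SF-36, CCFI and "Fecal Incontinence Quality of Life Scale (FIQoL) at 1, 3, 6 and 12 months from baseline".

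Section VI.c names one method for these: "Comparison of treatment effect over time (i.e., 1- and 3-, 6- and 12 months) on all scale scores will be performed" with a longitudinal linear mixed model. Its content is described only by what is random: "subject specific baseline levels and the time dependent response trajectories (i.e., slopes) random (SAS proc mixed"). VI.c does not state the fixed effects, whether time is continuous or categorical, any contrast at a given visit, or whether the baseline score is an outcome or a covariate. The only other named test is the t-test on the 1-month change, which is the primary analysis.

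**The concern.** Random baseline levels plus random slopes most naturally suggests a line for each patient, starting at baseline. The background in section I.b describes a different course: "The injected muscles become weak over 2-20 days and may recover over 2-4 months". Onset therefore falls before the first follow-up visit.

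What happens afterwards is uncertain. In the cited randomized comparison that used 100 IU, 75% of the Botox arm had improved at 1 month, and "The symptomatic improvement persisted at 1 year in 30% of patients in the biofeedback group, 35% in the Botox group". In the cited 60 IU series, at an average of 39 months, "there was no symptomatic recurrence in any of the 24 patients", although some had been retreated. Whether the benefit lasts or fades, a line starting at baseline has to spread an early step over 12 months.

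At stake is the trial's evidence on durability. An arm difference read from such a line could be too small early and too large late. A test of the slope difference asks whether the arms diverge over time, which is not the listed endpoint.

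**Working it through.** **The plan's own figures (VI.d).** The design decrease is 15 - 11.4 = 3.6 points. Forty completers gives 20 per arm. No SD is stated, so the 80% power cannot be reproduced directly. Solving for it, 3.6 points with 20 per arm and a two-sided 5% t-test needs an SD of about 3.96.

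**Assumptions, not in the documents.** The 3.6 points is taken as the ODS-S arm difference at month 1 (no placebo change). Data are complete, 20 per arm. Between- and within-subject SDs are both 2.8, so the SD of a change is sqrt(2) x 2.8 = 3.96, matching the figure above. Slope SD is 0 to 0.3 points per month. Three true courses at months 1/3/6/12:

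- (a) sustained: -3.60/-3.60/-3.60/-3.60
- (b) fading in the ratio 75% to 35%, that is -3.6 x (75 - 40(m - 1)/11)/75: -3.60/-3.25/-2.73/-1.68
- (c) lost after month 3: -3.60/-3.60/0/0

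**Linear time with baseline as an outcome.** With complete balanced data the expected fit is the least-squares line through the arm differences d at t = 0, 1, 3, 6, 12, whatever the variance components. Mean t = 4.4 and Sxx = 93.2. Slope = sum[(t - 4.4)d]/93.2; intercept = mean d - 4.4 x slope.

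- (a) slope = -15.84/93.2 = -0.170; intercept = -2.88 + 0.748 = -2.132
- (b) slope = -0.346/93.2 = -0.004; intercept = -2.236
- (c) slope = 17.28/93.2 = +0.185; intercept = -1.44 - 0.816 = -2.256

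| Course | Month 1 | Month 3 | Month 6 | Month 12 |
|---|---|---|---|---|
| (a) fitted (true) | -2.30 (-3.60) | -2.64 (-3.60) | -3.15 (-3.60) | -4.17 (-3.60) |
| (b) fitted (true) | -2.24 (-3.60) | -2.25 (-3.25) | -2.26 (-2.73) | -2.28 (-1.68) |
| (c) fitted (true) | -2.07 (-3.60) | -1.70 (-3.60) | -1.14 (0) | -0.03 (0) |

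Each intercept is a spurious baseline arm gap of 2.1 to 2.3 points. The endpoint is change from baseline, which this model gives as slope x months. For (a) that is -0.17/-0.51/-1.02/-2.04; for (c) it is +0.19/+0.56/+1.11/+2.22, the wrong sign.

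**Linear time on post-baseline visits only.** Mean t = 5.5 and Sxx = 69. Courses (a) and (b) are linear over these visits and are recovered exactly. For (c), slope = 25.2/69 = 0.365 and the fits are -3.44/-2.71/-1.62/+0.57.

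**Power.** Noncentral t, 38 df, variance (2/20) l'(G + 2.8^2 (X'X)^-1) l for the line. The categorical change contrast has variance (2/20)(2 x 2.8^2 + t^2 x slopeSD^2). With baseline as a covariate, 2 x 2.8^2 is replaced by 15.68 x (1 - 0.5^2) = 11.76, on 37 df. Ranges run over slope SD 0 to 0.3.

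| Significant for Botox | Line from baseline | Change contrast | Baseline as covariate |
|---|---|---|---|
| (a) month 3 | 72-75% | 78-80% | 88-90% |
| (b) month 3 | 58-61% | 69-72% | 81-83% |
| (c) month 3 | 37-40% | 78-80% | 88-90% |
| (a) month 6 | 77-88% | 72-80% | 82-90% |
| (b) month 6 | 49-61% | 49-57% | 58-69% |
| (c) month 6, true difference 0 | 16-21% | 2.5% | 2.5% |
| (a) month 12 | 69-93% | 55-80% | 61-90% |

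The slope test favours Botox in 24-44% of trials under (a). Under (b) it rejects in about 5% two-sided, the null rate.

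**The case against.** The strongest reply is that the misfit depends on text that is not there. Baseline levels and slopes in VI.c say what is random, not what the mean model is. A categorical arm-by-visit model with a random intercept and slope satisfies the sentence. The sentence also lists four post-treatment visits and not baseline, and a line through those four recovers courses (a) and (b) exactly. This stands: a reader might infer that the plan commits to a line from baseline, and the documents do not support that.

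It also stands that the line is not uniformly worse on power. It equals or exceeds the plain change contrast at month 6 in (a) and (b), although it understates the effect there, and exceeds it at month 12 in (a), where it overstates.

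The courses are assumed too. The 2-20 days and 2-4 months describe muscle weakness, not symptom scores. The 75% and 35% are responder rates in one arm of a study without placebo. The lasting result comes from a 60 IU series in which 9 of 24 patients later received 100 IU.

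Finally, the planned means and SDs, with arm sizes, would let a reader work out an unadjusted arm difference. VI.c, however, names no such comparison for months 3, 6 or 12.

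What the reply does not remove is that models compatible with the sentence give very different answers. Under (c), the month-6 difference is estimated as -1.14, -1.62 or 0 depending on an unstated choice, and both lines are wrong.

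**Conclusion.** The point holds in conditional form. VI.c leaves the estimate for the visit-by-visit secondary endpoints undefined. If it is implemented as linear time with baseline as an outcome, the arm difference is misestimated whenever the effect begins before month 1. With a 3.6-point effect, the line understates months 1 and 3 by about 1.0 to 1.9 points in all three courses. It overstates month 12 by about 0.6 in (a) and (b), and month 6 by 1.1 in (c). If only post-baseline visits enter the line, the error is confined to courses that are not linear after month 1, such as early loss.

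The line fits themselves depend only on the assumed courses and complete data; the power figures also depend on the assumed SDs. An effect that really grew linearly from baseline would be estimated without bias. A reader might also infer that the main result is at risk. It is not: the primary 1-month comparison is a t-test that does not use this model. This is a worthwhile improvement to the secondary analyses, not a fault in the primary one.

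**What to change.** In VI.c, state that post-baseline scores are modelled with arm, visit as a categorical factor, arm-by-visit interaction and the baseline score as a covariate, keeping the random intercept and slope or using an unstructured covariance. Report the arm difference with 95% CI at 1, 3, 6 and 12 months as the secondary result. Any slope difference should be supplementary and labelled as change in the effect over time. Settle this before unblinding.

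The cost is wording only: same data, same SAS procedure, no change in sample size. The model has a few more parameters and somewhat less power if the post-baseline course really is linear. At month 3 under (b), power is 81-83% against 85-87% for a line through the post-baseline visits.

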On the day of the procedure, the research nurse will obtain the saline or Botox from the research pharmacy in a brown paper bag. She will then prepare the Botox or draw the normal saline and give it to the investigator for administration. In order to protect blinding, placebo and Botox will have the same characteristics, except for the active drug. The nurse who prepares the drug will also record the study arm in a file kept separate from patient information. Once this is recorded, information will be resealed and kept with patient information until the completion of the study. The nurse who prepared the composition will be the only unblinded member of the healthcare team and will not assist in the procedure.

The adverse effects will be assessed by one standard questionnaire, which allows the description of idiosyncratic reactions and 2 validated questionnaires, which assess the Botox specific adverse effects of fecal incontinence. Outcome measurements and assessment of adverse effects in the office will be made by a research nurse blinded to treatment group allocation.

The PI who delivers the intervention will not take outcome measurements and will have no interaction with the data collectors. The data collectors will be blinded throughout the data entry and data cleaning processes. The statistical analysis will be made after the end of the data collection period. The statistician will only be unblinded once the database is locked. At the end of the study, blinding integrity will be evaluated in a sample of participants and data collectors.

In case of medical emergency, if a study participant has encountered an urgent medical problem and the clinician needs to know his/her intervention group, the allocation code can be broken. Unblinding envelopes (labeled with the randomization number that contains allocation) are sealed by the study center and are only opened if emergency unblinding is necessary.

V. STUDY PROCEDURES

a. Study visits and parameters to be measured

As part of this research study, patients will be asked to come for three visits (Visit 1= return of informed consent and schedule of intervention; Visit 2= intervention; Visit 3=one month after the intervention). They will afterwards be contacted by mail with questionnaires and then with follow-up phone calls (for those who did not return questionnaires) to increase response rate at 3, 6 and 12 months after the intervention.

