month visit after the intervention. Also, we will send a letter to each patient when we receive the results, informing him/her of the overall outcome of this study.

e. Radiation Risks

Not applicable

VIII. POTENTIAL BENEFITS

a. Potential benefits to participating individuals

For patients specifically, the potential benefits include an improvement of chronic constipation symptoms and quality of life with a minimally invasive treatment.

b. Potential benefits to society

For society, the potential benefits are great. At this time, few minimally invasive, easily to administer outpatient options for the treatment of ODS are available. The standard of care (biofeedback) is only available in a few select centers across the country and is not a "quick fix" taking multiple sessions to make progress. These may or may not accept the patients' current insurance. On the other hand, the incidence of chronic constipation in the US population is clearly on the rise, as the baby boomers are reaching their 60s. Botox, should it be effective, could alleviate the profound suffering and discomfort associated with this condition. It could also provide an accessible and fast-acting option for the treatment of ODS.

IX. MONITORING AND QUALITY ASSURANCE

a. Independent monitoring of source data

Monthly meetings will be organized to allow monitoring of recruitment of patients, and to assure that the IRB protocols are adhered to. The results of the study will be reviewed at 1/2 of recruitment goals. The study will be halted if a particular study arm appears to be more efficacious or if any unanticipated adverse events occur resulting in serious morbidity or mortality.

b. Safety monitoring

We do not expect any unusual safety concerns in this study as all of the treatments and procedures planned are FDA-approved for a different indication and are thought to be extremely safe.

c. Outcomes monitoring

The principal investigator will monitor completeness of data and assure the validity and integrity of data and adherence to the IRB-approved protocol. She will also review the accuracy and

completeness of case report form entries, source documents and informed consent. IRB will be notified of any major unforeseen complications associated with the study.

d. Adverse event reporting guidelines

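### The half-way efficacy halt has no endpoint, boundary or reviewer, no allowance in the final 0.05 test, and conflicts with the rule that analysis follows data collection

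*Combined protocol and SAP*

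**What the plan says.** Section IX.a (independent monitoring of source data) states "The results of the study will be reviewed at 1/2 of recruitment goals" and then "The study will be halted if a particular study arm appears to be more efficacious". The same sentence also provides for a halt on serious unanticipated adverse events; that part is not at issue here. No endpoint, test, threshold or decision-maker is given for the efficacy halt.

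Section VI.c mentions no interim analysis and sets one criterion: "All p-values are two-tailed and considered significant if p<0.05". Section VI.d sizes the trial at 46 patients, expects attrition of up to 15% ("we anticipate to attain 40 study completers"), and claims its effect can be detected "after treatment with Botox with 80% power at a 5% significance level".

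Section IV.c says "The statistical analysis will be made after the end of the data collection period" and "The statistician will only be unblinded once the database is locked". It adds: "The nurse who prepared the composition will be the only unblinded member of the healthcare team". The same section keeps the allocation list with the research pharmacy and the unblinded nurse. Neither is given the task of comparing arms.

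**The concern.** A rule that must end the trial when one arm looks better gives a second chance to declare a difference. If the final test stays at 0.05, the overall false-positive rate exceeds 5%, by an amount that depends on how strictly the rule is read. Nothing in the plan fixes that reading, so whoever conducts the review sets the error rate while looking at the results. They could also choose the outcome: section VI.b makes the primary endpoint a change in the sum of two scores, section VI.c describes comparing the two scores without mentioning the sum, and many secondary measures follow.

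A lenient reading does harm in one of two ways. If the halt counts as a positive result, false positives rise. If the roughly 20 completers in hand are then tested at 0.05, power is lost. A trial halted on a significant difference at that size also tends to overstate the effect on patient-reported scores.

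There is an operational conflict too. Judging which arm is ahead at half of recruitment requires an arm comparison before data collection ends, and section IV.c puts the analysis after it.

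**Working it through.** **Inputs.** From section VI.d: 23 per arm, 40 expected completers (20 per arm), 80% power, 5% level, and a fall in mean ODS-S from 15 to 11.4 (3.6 points). From section VI.c: t-test, two-sided 0.05. From section IX.a: one look at half of recruitment, taken here as 10 completers per arm, or half the information. Assumed, because the plan gives none: the interim p-value bar.

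**The plan's own figure.** 46 × 0.85 = 39.1, close to the 40 completers stated. No SD is given, so the 80% cannot be reproduced. Solving the two-sided t-test for 20 per arm and 80% power gives a difference of 0.909 SD, which implies an SD of 3.6 / 0.909 = 3.96 points. The power figures below use 0.909 SD, so they take the 80% as given.

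**Type I error.** The statistics at the two looks have correlation √0.5 = 0.707. With critical values c₁ (interim bar) and c₂ = 1.96 (final 0.05), the overall error when a halt counts as positive is

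α = 1 − P(|Z₁| < c₁ and |Z₂| < c₂).

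If the bar b is looser than 0.05 and the data in hand are then tested at 0.05, halts with p between 0.05 and b no longer count. They have null probability b − 0.05, so α falls by that amount: 12.5% − 5.0% = 7.5% at b = 0.10, and 21.6% − 15.0% = 6.6% at b = 0.20.

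| Interim bar | Halt counts as positive | Data in hand tested at 0.05 |
|---|---|---|
| p<0.001 | 5.0% | same |
| p<0.01 | 5.5% | same |
| p<0.05 | 8.3% | same |
| p<0.10 | 12.5% | 7.5% |
| p<0.20 | 21.6% | 6.6% |

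A simulation of t-tests (400,000 trials, 10 then 20 per arm) agrees: 8.4% at p<0.05, and 7.6% and 6.6% for the last two entries of the right-hand column.

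**Power at 0.909 SD (simulation).** With no look, 80%. Halting at p<0.10 and then testing the data in hand at 0.05 gives 70%; halting at p<0.20 gives 60%. With p<0.05 at both looks, power rises to about 82%. If the halt itself counts as positive, it is about 84% (p<0.10) or 87% (p<0.20), bought with the error rates above.

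**Overstatement, assuming an interim bar of p<0.05.** With a true difference of 0.5 SD (assumed), trials halted in the right direction report 1.11 SD on average, against 0.83 SD for trials significant at the end with no look. With a true 0.909 SD the figures are 1.26 and 1.02 SD.

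**Timing and blinding.** Set side by side, section IX.a needs an arm comparison at half of recruitment, while section IV.c puts the analysis after data collection and the statistician's unblinding at database lock. No text reconciles the two, and no coded-arm review is described.

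**The case against.** The strongest reply is that the size of the harm depends on a threshold the documents do not state. That is correct. With a bar of p<0.001 the excess over 5% is negligible, and power falls only if the bar is looser than 0.05 and the truncated data are then tested at 0.05; in other scenarios power rises. So the fair charge is that error and power are not secured, rather than that they are wrong by a known amount. This does not remove the fault: every bar examined gave more than 5% with the final test left at 0.05, and the missing bar is itself the defect.

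The overstatement figures compare halted trials with completed ones. Halts at p<0.05 occur in about 18% of trials at a true 0.5 SD and 48% at 0.909 SD. Over all significant trials the contrast is smaller: 0.94 against 0.83 SD, and 1.11 against 1.02 SD. The larger figures describe only a trial that has been halted.

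Section IV.c could be read as describing the final analysis only, and a comparison of coded arms would leave the statistician blinded. But the plan describes no such review, and it would still come before the end of data collection.

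Finally, the review is triggered by recruitment, while the primary outcome comes a month after treatment, so less than half the information may be in hand. At 30% to 40% information, the fixed limits offered under the fix give about 5.1% (O'Brien-Fleming) or 5.2% to 5.4% (Pocock). That drift is small, but the timing should be stated.

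**Conclusion.** The concern holds and must be fixed. The plan contains a mandatory efficacy halt that its error rate and sample size ignore and that its timing and blinding rules do not accommodate. Under the scenarios examined, type I error runs from 5.0% (a very strict bar) through 8.3% (nominal 0.05 at both looks) to 21.6% (p<0.20 with the halt counted as positive). Power can fall to 70% or 60% when a loose halt is followed by a test at 0.05. These figures assume looks at half and full information with 10 then 20 completers per arm; the power figures also assume a true difference of 0.909 SD. The missing SD is a separate gap: the 80% could not be checked even without the look. The contradiction between sections IX.a and IV.c, and the absence of any interim provision in section VI, rest on the text alone.

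**What to change.** **Preferred.** In section IX.a, delete the efficacy condition from the halting sentence and leave the adverse-event wording as it is. State that the half-way review covers safety, plus recruitment and data completeness pooled over arms, with no efficacy comparison by arm. The final 0.05 in section VI.c and the timing and unblinding rules in section IV.c then stand unchanged. The cost is protocol wording and the loss of a possible early efficacy stop in a 46-patient trial.

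**If an efficacy stop is wanted.** Name the endpoint and an alpha-controlling boundary. For one look at half information, examples are O'Brien-Fleming (p<0.0052, then p<0.048) or Pocock (p<0.0294 at both looks); each holds 5.0%. State how many one-month outcomes must be in hand before the look, or use an alpha-spending function. Say who makes the comparison and how the blind is kept, and amend sections IV.c, VI.c and VI.d to match. At 0.909 SD, O'Brien-Fleming lowers simulated power only from 79.9% to 79.6%; Pocock gives 75.6% by the normal calculation, against a planned 80%. A boundary does not remove overstatement in trials that stop: at a true 0.5 SD, about 3.7% would stop under O'Brien-Fleming and report about 1.37 SD on average.
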